### **13. ALTERNATIVES TO STUDY PARTICIPATION**

Potential study subjects may simply decline enrollment.

### **14. POTENTIAL RISKS**

1. Infection. There is the potential risk of infection since subjects will have a probe inserted through the skin. Since there will be nothing left going through the skin or in the subject after the probe is withdrawn, the risk of infection is very small and there has never been a report of permanent injury due to infection following cryoneurolysis.
2. Bleeding. The probe does not have an open tip and is not particularly sharp, so there is a very low risk of having any type of bleeding as a result of treatment. However, if it was to happen, we would hold pressure until the bleeding stopped.
3. Falling. The risk of falling due to cryoneurolysis in a lower extremity (leg) currently unknown, although it has never been reported in the medical journals. Subjects will be provided with a pair of crutches following treatment if desired, although it is rare that an individual feels the need to use crutches to walk.
4. The skin where the nerve is frozen could lose or gain color if the nerve is particularly close to the surface. However, this has never been reported for deeper nerves and using the probe that will be used for this study.
5. Since a nerve will be frozen, there is the chance of nerve injury. However, in 5 decades of use, only a single case of "neuritis" (nerve irritation) has been reported in medical journals, and this went away after a few months.
6. There is the risk of loss of confidentiality. The following procedures will be done to maintain confidentiality: written, paper forms will be kept in a locked medical office and the locked Investigational Pharmacy's files. Computerized records containing personal health information will be stored on password-protected and encrypted computers.

### **15. RISK MANAGEMENT PROCEDURES AND ADEQUACY OF RESOURCES**

During the treatment, subjects will be continuously monitored with pulse oximetry, noninvasive blood pressure cuffs, and EKG (standard for catheter placement). Subjects will receive an IV so that emergency medications could be given, if needed. As described above, probes will be placed under sterile conditions as is standard-of-care for any percutaneous cryoneurolysis.

Following treatment, the subjects will be contacted at least the day following treatment by an

investigator or research coordinator, and longer if the subject desires or if medically indicated (e.g., suspected possible infection). Subjects will have a physicians' pager and cellular phone numbers available to respond 24 hours/day and 7 days/week for at least the first week following treatment.

The risks to confidentiality are the release of names/ telephone numbers/ demographic data (e.g. weight, age, height), which will be minimized by the use of password-protected computers and case report forms that will be stored in locked offices.

Subjects will be given clear instructions to call an investigator with any questions or concerns regarding their study participation. If a patient experiences an injury that is directly caused by this study, only professional medical care that they receive at the medical center. No other compensation is offered. Any adverse events will be reported to the IRB using the standard adverse events reporting and upon continuing review (depending on severity, as defined by the IRB).

The study Data Safety Monitoring Board (DSMB) will be comprised of the Medical Monitor, a physician experienced in both clinical trial management and the ethical conduct of research, and a statistician, also well-experienced in multicenter trials. All three of these individuals will be completely independent of the investigative team. No member of the DSMB will have any financial, proprietary, professional, or other interests that may affect impartial, independent decision-making by the DSMB. The board will comprise individuals with no vested interest in the outcome of the research study. The members will also sign a confidentiality statement. The DSMB will operate from a charter describing its role, membership, reporting procedures, and meeting protocol. The DSMB will decide on its own protocols, set triggers for data review or analyses, and establish guidelines for monitoring the study, stopping the study for safety concerns, and for efficacy based on plans specified in the protocol. Confidentiality will be maintained during all phases of DSMB review and deliberations. DSMB members will maintain strict confidentiality concerning all privileged trial results provided to them. The board will perform the following functions:

- Approval of the trial protocol before enrollment of patients
- Review the data in order to determine efficacy, futility, and safety, and to determine whether the study should continue
- Review data quality and data integrity
- Evaluate risk versus benefit by thorough examination of the data accumulated
- Determine whether the trial is proceeding as planned, the protocol is being followed, the recruitment of patients is on schedule, and data are being collected with the proper accuracy
- Review patient dropouts, if any, and make appropriate recommendations
- Determine whether safety concerns have been raised by the experimental or control treatments

**Review Items.** Items to be reviewed by the DSMB include:

- Interim/cumulative data for evidence of study-related adverse events
- Interim/cumulative data for evidence of efficacy according to pre-established statistical guidelines in the study protocol
- Data quality, completeness, and timeliness
- Performance of individual centers
- Adequacy of compliance with goals for recruitment and retention, including those related to participation of women and minorities
- Adherence to the protocol

- Factors that might affect the study outcome or compromise the confidentiality of the trial data (such as protocol violations etc.)
- Factors external to the study such as scientific or therapeutic developments that may impact participant safety or the ethics of the study

**Recommendations.** The DSMB will conclude each review with their recommendations to the principal investigator and primary site Institutional Review Board (at the University of California San Diego) as to whether the study should continue without change, be modified, or terminated.

Recommendations regarding modification of the design and conduct of the study may include:

- Modifications of the study protocol based upon the review of the safety data
- Suspension or early termination of the study or of one or more study arms because of serious concerns about patients' safety, inadequate performance, or rate of enrollment
- Suspension or early termination of the study or of one or more study arms because study objectives have been obtained according to pre-established statistical guidelines
- Optional approaches for executive committee and investigators to consider when the DSMB determines that the incidence of the primary study outcomes is substantially less than expected, such as recommendations to increase the number of trial centers or extend the recruitment period
- Corrective actions regarding a study center whose performance appears unsatisfactory or suspicious

Appropriate reports will be made to the Institutional Review Boards at all enrolling centers and the executive committee, comprised of all co-investigators and site directors

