### Civilian university medical centers:

- Cleveland Clinic, Cleveland, Ohio
- University of California San Diego, San Diego, California

- University of Florida, Gainesville, Florida

All protocols and study materials will be approved by each center's Institutional Review Board; and, the study will be prospectively registered on the clinicaltrial.gov website. The study will be overseen by both a medical monitor ([name], PhD; Case Western Reserve University; Cleveland, Ohio)—in essence a study subject advocate—as well as a Data Safety Monitoring Board comprised of the medical monitor, a physician familiar with the ethical conduct of clinical research, and statistician. The Medical Monitor is responsible to oversee the safety of the research and report observations/findings to the IRB or a designated institutional official. The Research Monitor will review all unanticipated problems involving risks to subjects or others associated with the protocol and provide an independent report of the event to the IRB. The Research Monitor may discuss the research protocol with the investigators; shall have authority to stop a research protocol in progress, remove individual human subjects from a research protocol, and take whatever steps are necessary to protect the safety and well-being of human subjects until the IRB can assess the monitor's report; and shall have the responsibility to promptly report their observations and findings to the IRB or other designated official and the Human Research Protections Office. The medical monitor and DSMB will review enrollment, study data, protocol violations, adverse events, and oversee all aspects of the clinical trial every one and six months, respectively, through data analysis. All procedures are considered experimental given these are volunteers and they would not receive these treatments without study participation—while cleared by the FDA for use in all chronic and acute pain states, cryoneurolysis has not been demonstrated as effective to treat phantom limb pain, and it is not considered “standard-of-care” at either UCSD or other institutions.

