**Optional crossover treatment.** Four to six months following the initial treatment, subjects **may** return for an optional repeated intervention procedure (“crossover”) with the alternative treatment (either active cryoneurolysis or sham/placebo), again in a double-masked fashion using the same protocol as described for the initial intervention. **The crossover treatment is not required for study participation, as the primary analyses will include a parallel study design for the initial intervention evaluated prior to any crossover treatment.** However, an optional crossover treatment will be offered to subjects for two reasons: (1) it will ensure that all subjects have access to the proposed treatment, regardless of the treatment they are initially randomized to; and, (2) it will permit intra-subject differences between treatments to be analyzed (e.g., assessing treatment-effect heterogeneity, or the variability of the causal effect across individuals, which would not be available from the parallel-group portion of the study alone). These intra-subject differences will be secondary analyses, as there may be patient-selection bias regarding which subjects decide to have the crossover treatment (e.g., if the intervention is successful at greatly reducing phantom limb pain, then subjects receiving active cryoneurolysis during their initial treatment will be more likely to forgo the crossover treatment). This crossover will **not** affect the primary analyses, which will involve a parallel group study design and investigate the effects of cryoneurolysis within 4 months of the initial intervention. The approximate duration of a crossover visit will total 2-4 hours, from the time the subject enters the treatment facility until the time the depart.

Following study completion, the results will be mailed to all enrolled subjects in written form using non-technical (i.e. “layperson”) language.

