**Outcome measurements (endpoints).** We have selected outcome measures that have established reliability and validity, with minimal inter-rater discordance, and are recommended for chronic pain clinical trials by the Initiative on Methods, Measurement, and Pain Assessment in Clinical Trials (IMMPACT) consensus statement. ***The primary end point will be the difference in average daily phantom pain intensity at baseline and 4 months following the initial intervention (measured with the NRS as part of the Brief Pain Inventory).*** The primary analyses will compare the two treatments (inter-subject comparisons) during the initial treatment period in which half of the subjects will receive active cryoneurolysis and the other half a sham/placebo treatment. Endpoints will be evaluated at baseline and post-treatment (Day 0), Days 1 and 7; and Months 1, 2, 3, 4, and 12,

(Table 1). These same time points through Month 4 will be evaluated following the optional second (crossover) treatment.

The questionnaire will differentiate among multiple dimensions of limb pain:

**Residual limb (“stump”) pain:** painful sensations localized to the portion of limb still present.

**Phantom limb sensations:** non-painful sensations referred to the lost body part.

**Phantom limb pain:** painful sensations referred to the lost body part.

Each type of pain/sensation will be defined for subjects immediately prior to questionnaire application at each time point, and subjects will be instructed to specifically address phantom limb pain when responding to the various questions. In addition, since there is a strong correlation between phantom and residual limb pain, we will specifically inquire about both types of pain. Each time the questionnaire is applied, subjects will be instructed to respond for the previous 3 days (e.g., worst pain during the previous 3 days) because studies have suggested that patients have “increasing difficulty actually remembering symptom levels beyond the past several days.” Exceptions will be on Day 1 for both the initial and crossover treatments because at these time points, the interest is in subjects’ experiences subsequent to the treatment and not prior to the intervention. During these two days, subjects will be instructed to respond for the period of time since their treatment.

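### The protocol does not say how falls, infections or other adverse events after Day 1 are to be elicited, although it ranks falling among the main risks and calls its size unknown

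*Combined protocol and SAP*

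**What the plan says.** **The risk.** Section 18 names infection and falling as the foremost risks. Section 14 says the risk of falls is not known, and adds that none has appeared in the journals. Section 7 expects a complete conduction block of 6-8 weeks from one procedure. The subjects are lower-limb amputees (Section 10), and both the sciatic and femoral nerves, or their branches, are treated (Section 9).

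**Safety contact.** Section 15 states that "the subjects will be contacted at least the day following treatment", and "longer if the subject desires or if medically indicated (e.g., suspected possible infection"). Section 9, Intervention, offers calls on Days 1-7 to answer questions, if the subject wants them or there is medical need. Physicians can be reached around the clock for at least the first week, and subjects are told to call with concerns.

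**Scheduled calls.** Section 9, Outcome measurements, sets assessments at Days 1 and 7 and Months 1, 2, 3, 4 and 12, and "These same time points through Month 4 will be evaluated following the optional second (crossover) treatment". The questionnaires are given by telephone from one central site. Table 1 and the text around it list the Brief Pain Inventory, residual limb pain, global impression of change, Beck inventory, phantom sensations, analgesic use and other pain locations. The treatment guess is asked on Day 0.

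**Handling of events.** Sections 15 and 18 send any adverse events to the IRB. Section 9 says "The medical monitor and DSMB will review enrollment, study data, protocol violations, adverse events" and other matters, monthly for the monitor and six-monthly for the DSMB. In Section 15 the DSMB is to "Determine whether safety concerns have been raised by the experimental or control treatments". One of its review items is "Interim/cumulative data for evidence of study-related adverse events", and it may recommend "Suspension or early termination of the study or of one or more study arms because of serious concerns" about patient safety.

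**Analysis.** The Statistical Plan covers efficacy, blinding, crossover, long-term follow-up, dropouts and interim looks. It has no summary of adverse events.

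**The concern.** The plan specifies who receives and reviews adverse events, but not how an event after Day 1 enters the record. On the text alone, that depends on extra contact being judged necessary, on the subject telephoning, or on the subject mentioning it during a call about something else. If few falls are recorded, a reader could not tell whether few happened or few were asked about. The existing reassurance, that the literature reports no falls, has the same weakness.

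Two things are at stake. The first is care: asking would bring a fall or infection to the treating site sooner. The second is information: a sham-controlled randomised comparison is a good opportunity to describe a risk that the protocol itself calls unknown.

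**Working it through.** No figure in the plan bears on this point, so there is none to reproduce. The check sets the text side by side and then costs the remedy.

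**1. Is there a safety item in the calls?**

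| Source | Content | Fall, infection or adverse-event item |
|---|---|---|
| Section 9, Table 1 | Pain, global impression, Beck, phantom sensations | None |
| Section 9, Additional pain-related data | Frequency and duration of pain and sensations, analgesic use, other pain, Day 0 guess | None |
| Section 9, Intervention | Calls on Days 1-7 to answer questions, as wanted or needed | None stated |
| Section 15 | Day 1 contact, then conditional; subject may call | Method of asking not stated |
| Section 9, Statistical Plan | Efficacy and blinding analyses | No safety summary |

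**2. How does the risk window compare with the contacts?** Conduction loss of 6-8 weeks is 42-56 days. After the assured Day 1 safety contact, 42 - 1 = 41 to 56 - 1 = 55 days remain. Scheduled calls at Day 7, Month 1 and Month 2 fall in or near that window, so contact exists; what is missing is a stated question.

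**3. Could the pain items stand in for it?** Only in part. Section 9 sets a 3-day recall period for the questionnaire. Taking a month as 30 days (an assumption), the Day 7 and Month 1 calls cover 2 x 3 = 6 of the 41-55 days. Month 2, at about day 60, looks back to days 58-60, after the window has closed. A painful injury or infection that persists to a call could surface through the residual limb or other-pain items. A fall without lasting pain would not be asked about. This describes what the items cover; it does not estimate missed events.

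**4. What would asking cost?**
- Calls after the initial treatment: Days 1, 7 and Months 1, 2, 3, 4, 12 = 7.
- Calls after crossover: Days 1, 7 and Months 1, 2, 3, 4 = 6, giving 7 + 6 = 13 in total.
- At the maximum of 144 subjects: 144 x 7 = 1,008 calls if nobody crosses over; 144 x 13 = 1,872 if all do. The documents give no crossover uptake, so these are the two ends.
- At an assumed 1-2 minutes: 1,008/60 = 16.8 to 33.6 hours; 1,872/60 = 31.2 to 62.4 hours.
- Per call: 1/15 = 6.7% to 2/15 = 13.3% of a standard 15-minute call. Where the Beck inventory adds 15 minutes, it is 1/30 = 3.3% to 2/30 = 6.7%.

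Sample size, alpha and power do not change.

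**The case against.** The strongest reply is that silence in these lists proves little. Table 1 is headed a summary, and the text after it adds items the table lacks, so neither is a full call script. Case report forms and a DSMB charter are mentioned but not supplied, and the DSMB sets its own triggers and safety guidelines. This stands, and it limits the point to what the protocol text says.

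A second reply is that oversight is already broad. A reader might infer that safety is not monitored, or that the DSMB would see only events judged related to the study. The documents support neither. Any adverse events go to the IRB, and Section 9 has the monitor and DSMB review adverse events without a relatedness limit; the narrower wording is one item in a list. But review acts on events already captured, so it does not answer how they are captured.

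A third reply is that subjects are not lost after Day 1. That is also correct: a reader might take Section 15 to mean that contact ends there, but the routine calls assure later contact.

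Finally, a descriptive table by arm could be made from recorded events without being planned in advance. That is so, and its absence alone would be a reporting detail. Prompting also carries some risk to masking, which is checked only on Day 0.

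**Conclusion.** The point holds in a limited form. The protocol names falling and infection as its main risks and calls the fall risk unknown, yet does not state how events after Day 1 are elicited, although calls to every subject are already scheduled. Followed as written, the plan would tend to under-capture that risk. It is a cheap improvement, and the primary pain result is unaffected.

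The size of any under-reporting cannot be computed from the documents. A reader might try to size it with an upper confidence limit for zero observed events, but such a limit reflects the number of subjects, not the missing question, so it does not measure this gap. Nor do the documents show that events will go uncollected, only that the method is not stated.

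Confidence is medium, because the scripts and forms were not available. If they already contain the question, what remains is a sentence in the protocol and the summary by arm.

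**What to change.** At each existing call (Days 1 and 7, Months 1, 2, 3, 4 and 12, and the crossover calls), after the pain and global-impression items, ask one short neutral prompt. It should cover the whole period since the last call, not the 3-day recall period:
- any fall, with date and injury;
- any infection or problem at the treatment site;
- any other new health problem or unplanned medical contact.

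Do not name numbness or weakness before the Month 4 endpoint is recorded; note them if volunteered. Enter answers on a REDCap form and send positive answers to the treating site director and the medical monitor, because the callers sit at one central site.

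In the Statistical Plan, add a descriptive summary of all recorded events by randomised arm through Month 4, regardless of judged relatedness, and by treatment received afterwards. Give the same summary to the DSMB.

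The cost is the staff time worked out above, one form and one table shell, with no new visits. Recorded event counts may rise in both arms. A small risk remains that an answer unmasks the caller or subject before the self-reported Month 4 endpoint. Neutral wording and asking last reduce that risk but do not remove it.

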## 16. PRIVACY AND CONFIDENTIALITY CONSIDERATIONS INCLUDING DATA ACCESS AND MANAGEMENT

**Disposition of data.** The original, hard-copy signed informed consent forms and case report forms will be stored within the local site director's locked office, where they will remain for at least 7 years. These hard copies will not be mailed or otherwise transferred. Data will be uploaded and stored in one location: the central servers of Department of Outcomes Research at the Cleveland Clinic, a department dedicated completely to clinical research. This department has a full-time Research Electronic Data Capture (REDCap) programmer dedicated to developing REDCap databases and providing support for clinical trials. REDCap is a relational database for data entry and auditing. This is a web-based application designed exclusively to support data capture for research studies. The Department of Outcomes Research at the Cleveland Clinic web servers are encrypted and password-protected with multiple firewalls to the standards of the National Institutes of Health. Of note, the servers are backed up every night. In the case of a disk failure, only data written to the files since the last backup will be subject to loss and can be easily restored. Databases are protected through electronic measures using a multi-layered, but simple approach: all study related files will reside on the database server rather than on individual hard disk drives and the files will be protected by the operating systems features against general access. User names will be password protected. The electronic data will remain within the Department of Outcomes Research for 7 years following study completion. The UCSD research coordinator may receive training at the UCSD CTRI in REDCap use. With such training, up to six hours of user support is provided without recharge. However, technical and most user support will be provided by the Cleveland Clinic. The USAMRMC (United States Army Medical Research and Materiel Command) is eligible to review study records at any time.

Each local site will transfer certain PHI to the UCSD research coordinator who will make all data

collection phone calls for all subjects. PHI transferred will include the subject's name, phone numbers, and study ID. This information will be transferred via a secure online system known as the Army Missile and Research, Development and Engineering Command Safe Access File Exchange System (AMRDEC SAFE). AMRDEC SAFE is a secure, password-protected, system that the military has approved, and requires, for the transfer of such data. Civilian centers may use this system if access is granted, or fax to a locked office with access restricted only to the UCSD study coordinator and the PI.

**Sharing study results.** Following study completion, all subjects will be provided with the study results in written form and in language appropriate for non-medical individuals. In addition, the master dataset will be de-identified.

